7.6.4 Autoantibody screen

Blood samples will be sent to the central laboratory at the Screening Visit (Visit 0) for anti-nuclear antibody immunofluorescence and to detect the presence of SSc-associated anti-nuclear autoantibodies, such as anti-Scl-70 (anti-topoisomerase 1), anti-RNA polymerase III, and anti-centromere.

7.6.5 Blood pressure and heart rate measurement - amended

Blood pressure and heart rate will be measured at all visits with the patient in a sitting position, after the patient has been at rest for 5 minutes. The same arm is always used for these measurements.

At certain visits where a blood sample for PK is scheduled after the morning dose of study medication, an additional vital signs measurement (blood pressure and heart rate) will be taken within 20 minutes prior to PK sampling. Please refer to Section 7.1.1.

Methodology: Noninvasive measurement preferably with a validated electronic device in accordance with published guidelines (eg, American Heart Association Recommendations for Blood Pressure Measurement in Humans and Experimental Animals [25]).

Assessment of orthostatic changes¹¹⁶

To assess orthostatic changes, blood pressure and heart rate will be measured with the patient in a supine position, after the patient has rested for 5 minutes. Immediately thereafter, the patient should sit up and blood pressure and heart rate will be measured after the patient has rested for 2 minutes.

These measurements should be performed approximately 2 hours after study medication intake.

Frequency: Visit 11 (Week 39), Visit 12 (Week 52), during the Dose-Titration Period of the Long-Term Extension Phase (Visits 13 to 17).

7.6.6 Modified Rodnan skin scoring (mRSS)

The mRSS is a validated physical examination method for estimating skin induration. It correlates with biopsy measures of skin thickness and reflects prognosis and visceral involvement, especially in early disease. It is scored on 0 (normal) to 3+ (severe induration) ordinal scales over 17 body areas, with a maximum score of 51 and is used to categorize severity of SSc.[26] It has been extensively used as a primary and secondary outcome measure in randomized clinical trials.[27,28]

This assessment should be performed by a physician who is experienced and trained in skin scoring. To prevent inter-observer variability, the same physician must perform skin scoring for the same patient throughout the entire study.

Frequency: Screening Visit (Visit 0), Visit 7 (Week 12), Visit 10 (Week 26), Visit 11 (Week 39), Visit 12 (Week 52), and every 3 months thereafter in the long-term extension phase and termination visit.

¹¹⁶ Per Amendment 6

7.6.7 Electrocardiogram

Standard ECGs (12-lead ECG) will be recorded with the patient in the supine position after the patient has rested for at least 5 minutes.

All ECG printouts will be identified with the patient identification as well as date and time of recording and will be attached to the patient's file. All ECG printouts will be examined locally by the investigator on the day of recording for safety and quality. Any clinically relevant abnormality will be documented as an AE.

Electrocardiograms will then be transferred electronically and assessed centrally by an expert in cardiology who will provide expert assessment and interpretation of all ECGs obtained.

The name and address for the ECG service provider can be found in the documentation supplied by the vendor. Electrocardiogram procedures will be described in a separate manual.

Frequency: screening visit (Visit 0), Visit 1 (Day 0), Visit 7 (Week 12), Visit 10 (Week 26), Visit 11 (Week 39), Visit 12 (Week 52), every 3 months (12 weeks) in the long-term extension phase, termination visit and safety follow-up visit.

7.6.8 Pulmonary function testing

The following lung function measurements will be performed locally:

- FVC and % of predicted
- DL_{CO} (mmol/min/kPa) and % of predicted (hemoglobin-corrected)

Printouts from the analyzer must be stored in the patient file and the measured values transferred to the eCRF.

The hemoglobin value required for the pulmonary function tests performed at visits with limited assessments (see Section 7.1.2.10) will be measured at the local laboratory. The hemoglobin value will be entered in the eCRF and used for the calculation of predicted DL_{CO} only.¹¹⁷

Frequency: screening visit (Visit 0), Visit 7 (Week 12), Visit 10 (Week 26), Visit 11 (Week 39), Visit 12 (Week 52), and every 3 months (12 weeks) in the long-term extension phase and termination visit.

7.6.9 Skin biopsy

As stated in Section 7.6.3 above, biomarker analysis will be performed using skin and blood samples.

Skin biopsies will be obtained from the mid dorsal surface of the forearm (150 ± 20 mm proximal to the ulnar styloid) at Visit 1 (Day 0) and at Visit 8 (Week 14) and at a termination visit if this visit occurs before Visit 8.

If affected skin is located in that area, then the affected skin should be used. A biopsy should be performed regardless of whether or not affected skin is present. The skin biopsy obtained after treatment should be taken from the same arm, approximately 25 mm distance away from the initial biopsy, so as to avoid healing of the initial biopsy interfering with mRNA measurement. The location of the biopsy (right or left forearm) and distance from the ulnar

¹¹⁷ Per Amendment 4

styloid will be documented. If in the opinion of the investigator the mid dorsal forearm is not appropriate, another location can be chosen. The alternative site and the reason for changing the site will be documented.

At each time point (Visit 1 and Visit 8), two 4-mm skin punch biopsies next to each other will be obtained (one for RNA extraction and the other for histology/immunohistochemistry). The skin to be biopsied will be cleaned before biopsy and the remainder of the procedure will be performed using clean technique, per standard dermatological practice. The skin at the biopsy site will be marked by drawing a circle of about 10 mm diameter using a dermatological ink skin marker.

Skin will be biopsied with a 4-mm Baker style skin punch, provided by the Sponsor. The punch will be centered at the 10-mm diameter circle. The biopsy site will be closed by Steri-strips or sutures (at the discretion of the investigator) to provide hemostasis and ensure proper healing.

At the discretion of the investigator, patients may be instructed to apply a small amount of antibiotic ointment and a sterile bandage to the site daily; these supplies will be provided by the investigator. At the discretion of the investigator the biopsy site can be dressed with an appropriate dressing. If sutures are used the sutures will be removed after 5 to 14 days.

7.6.10 Digital ulcer net burden

Digital ulcers are defined as a full thickness skin lesion with loss of epithelium including lesions covered by eschar. Ulcers should be > 3mm in maximal diameter. Healing is defined by re-epithelialization with loss of pain and exudate. Pitting scars and hyperkeratotic lesions are always excluded.

Digital ulcer net burden will be assessed by the following methods:

- Ulcer count – this ideally will be performed by the same healthcare professional at every visit:
 - Total ulcer counts
 - Distal counts: distal (fingertip) – any ulcer including skin area distal to proximal interphalangeal (PIP) joint
- Ulcer burden:
 - Number of ulcers at time point minus baseline number of ulcers
- Visual analog score (VAS) for patient-reported severity of digital ulcers as part of the SHAQ (see section 7.6.13)

Frequency: Digital ulcer net burden assessment at every visit. VAS as part of SHAQ: Visit 1 (Day 0), Visit 8 (Week 14), Visit 10 (Week 26), Visit 11 (Week 39), Visit 12 (Week 52), Visit 18 (week 64), and every 3 months thereafter in the long-term extension phase and termination visit.

7.6.11 Digital gangrene

Digital gangrene will be recorded as a separate event and may co-exist with digital ulcers that affect the same digit and fulfil the criteria in section 7.6.10 above.

Gangrene is defined as diffuse necrosis (pathologic death of deeper, eg, subcutaneous structures) due to obstruction, loss, or diminution of blood supply; it is of black color and

painful, and may be localized to parts of the finger or involve an entire finger. It may be wet or dry, reflecting a degree of adjacent tissue perfusion, time course of necrosis and presence or type of associated secondary infection.

7.6.12 Raynaud's attacks assessment

Raynaud's attacks will be assessed using the composite of the following 6 individual outcome measures in order to minimize the measurement variability and placebo response: Raynaud's condition score, patient assessment of Raynaud's phenomenon, physician assessment of Raynaud's phenomenon, attack symptoms, duration of attacks, and average number of attacks per day.[29]

The Raynaud's condition score is a daily patient self-assessment of Raynaud's phenomenon activity using a 0-10 ordinal scale from 'no difficulty' to 'extreme difficulty'. It incorporates the cumulative frequency, duration, severity and impact of Raynaud's phenomenon attacks, reflecting the overall degree that Raynaud's has affected use of the patient's hands.[30]

The Raynaud's condition score, details of the frequency and duration of Raynaud's attacks, and attack symptoms of pain, numbness and tingling, each represented by a 0 – 100 VAS, will be incorporated into the daily diary that patients will be asked to complete for 7 days at the time points detailed below.

The patient and physician assessment measures the severity of Raynaud's phenomenon in the past week using a 0–100 VAS and will be assessed at the clinic visits outlined below.

Frequency: Daily diary to be completed by patient for 7 consecutive days leading up to Visit 1 (Day 0), and 7 consecutive days leading up to Visit 8 (Week 14). The patient and physician assessments of Raynaud's phenomenon will be performed at Visit 1 and Visit 8.

7.6.13 Patient-reported outcomes (PROs) / Health-related quality of life (HRQoL) questionnaires

Three PROs—the SF-36 v2.0, SHAQ, and UCLA SCTC GIT 2.0—will be completed by all patients in the study. The PROMIS-29 PRO will be completed by patients in a subset of sites belonging to English-speaking countries as this instrument has not yet undergone translation into multiple languages. To minimize bias, patients will be assured that all data will be treated confidentially, will not be reported to their patient files, and that the answers will not have any influence on study drug treatment. In addition, patients will complete the questionnaires on their own, or with the help of relatives, friends or study staff if restricted by digital lesions, before being seen by the clinician at the respective visit. Subsequently, a member of the site investigator's team will enter the responses into the eCRF.

Short Form 36 (SF-36) Questionnaire v2.0

The SF-36 is a multi-purpose, generic, HRQoL instrument that is composed of 1 multi-item scale that assesses 8 health concepts: physical function, physical role limitations, bodily pain, general health perceptions, vitality, social functioning, role limitations due to emotional problems, and emotional well-being.[31] The instrument has 36 items and requires approximately 5 minutes to complete.

Scleroderma Health Assessment Questionnaire (SHAQ)

The SHAQ consists of 8 domains from the HAQ-DI, a HRQoL instrument that measures self-reported function in 8 domains of activity in 20 weighted responses and a VAS of pain experienced in the past week. It additionally measures 5 domains specific to scleroderma using a continuous VAS: Raynaud's phenomenon, digital tip ulcers, lung symptoms, gastrointestinal symptoms, and a global patient assessment.[32] The VAS subscales of the SHAQ were shown to be significantly correlated with objective parameters,[32] and was responsive to change in a cohort and in a Raynaud's phenomenon trial in SSc.[30, 32] The SHAQ requires approximately 5 minutes to complete.

University of California, Los Angeles, Scleroderma Clinical Trial Consortium Gastrointestinal Scale (UCLA SCTC GIT) 2.0

The UCLA SCTC GIT 2.0 instrument is a self-reported PRO consisting of 34 items, which are revised from the 52-item instrument SSC-GIT version 1.0, and 7 multi-item scales that include reflux, distension/bloating, diarrhea, fecal soilage, constipation, emotional well-being, and social functioning. The validity and reliability of this tool has been supported in a study performed in individuals with SSc, which also demonstrated good symptom correlation with gastrointestinal diagnoses.[33] The UCLA SCTC GIT 2.0 requires approximately 2 minutes to complete.

Patient-Reported Outcomes Measurement Information System (PROMIS)-29

The PROMIS-29 is a validated instrument to measure the health status of SSc patients, demonstrating moderate to high correlation with other instruments validated in SSc, including the SF-36 physical component score and HAQ-DI.[34] It incorporates 7 core domains from the PROMIS questionnaire, which specifically relate to physical, mental, and social health aspects of chronic illness: pain, fatigue, depression, anxiety, sleep, and physical function, as well as one 11-point rating scale for pain intensity.[34] It contains 8 items with 29 weighted responses in total, and requires approximately 5 minutes to complete.

Frequency of all PROs: Visit 1 (Day 0), Visit 8 (Week 14), Visit 10 (Week 26), Visit 11 (Week 39), Visit 12 (Week 52), Visit 18 (week 64), and every 3 months thereafter in the main treatment phase and long-term extension phase and at a termination visit.

7.6.14 Tender and swollen joint count

This physician-reported tool evaluates 28 joints for swelling and tenderness. This outcome measure should be performed by the same physician to assess the burden of joint disease from SSc-associated polyarthritides and myopathy.

A sample form is shown in Appendix 14.3

Frequency: Screening Visit (Visit 0) and Visit 12 (Week 52) and termination visit (not needed after V12).

7.6.15 Patient's and physician's global assessment - amended

This tool incorporates a self-assessment and physician assessment on the patient's overall health in the prior 1 week using a 0–10 ordinal scale and a rating of overall SSc-related health transition compared with 1 month prior and 1 year prior.

Frequency: Visit 1 (Day 0), Visit 10 (Week 26) and Visit 12 (Week 52), termination visit (not needed after V12), and visits with limited assessments.¹¹⁸

7.6.16 Patient interference with skin assessment

This self-assessment evaluates the degree in which skin involvement has interfered with the patient's daily activities over the last month on an ordinal scale of 0 (does not limit activity) to 10 (very severe limitation).

Frequency: Visit 1 (Day 0), Visit 10 (Week 26) and Visit 12 (Week 52) and termination visit (not needed after V12).

7.6.17 Tendon friction rubs

Anatomical sites including the hands, wrists, elbows, shoulders, knees and ankles will be examined for the presence or absence of tendon friction rubs at the two time points detailed below.

Frequency: Visit 1 (Day 0) and Visit 8 (Week 14).

7.6.18 Oxygen saturation measurement using forehead pulse oximetry¹¹⁹

Oxygen saturation measurements will be performed in all subjects using non-invasive forehead pulse oximetry expressing the SpO₂ (peripheral oxygen saturation) percentage. At visits with blood pressure measurements to assess orthostatic changes, oxygen saturation will be measured pre-dose and post-dose (see [Table 7-2](#), [Table 7-3](#), and [Table 7-4](#)). At all other visits, oxygen saturation will be measured pre-dose only.

If the patient receives supplemental oxygen, the amount [L/min] will be recorded in the eCRF.

Frequency: Visit 9 (Week 20), Visit 10 (Week 26), Visit 11 (Week 39), Visit 12 (Week 52), Visits 13 to 17 (Week 54 to 62), Visit 18 to Visit n (Open-label Extension Period), Termination Visit, and 30-day Safety Follow-up.

7.7 Appropriateness of procedures / measurements

All safety and efficacy variables, as well as the methods to measure them, are standard variables/ methods in clinical studies and/ or clinical practice. They are widely used and generally recognized as reliable, accurate and relevant.

8. Statistical methods and determination of sample size

8.1 General considerations

All variables will be analyzed descriptively with appropriate statistical methods: categorical variables by frequency tables and continuous variables by sample statistics, ie, mean, standard deviation, minimum, median, quartiles (if data are clearly non-normal) and maximum.

If not mentioned otherwise, all statistical tests will be performed with a type I two-sided error rate of $\alpha=5\%$.

¹¹⁸ Per Amendment 5

¹¹⁹ Per Amendment 6

Statistical analyses will be performed using SAS (Statistical Analysis System); the version used will be specified in the statistical analysis plan (SAP).

8.2 Analysis sets - amended

Efficacy and safety analyses will be performed in patients valid for the full analysis set (FAS). This is defined as all patients randomized and treated with study medication. Investigators will be instructed not to make the call to the IxRS system until they are certain the patient is valid to be treated with study medication, on the day that study medication is to start. In that way, we expect all patients who are randomized also to be treated, so the FAS population would then be consistent with the full intent-to-treat (ITT) definition.

For the primary and secondary exploratory efficacy and safety endpoints, as a supportive analysis, a per protocol set (PPS) will also be defined, including patients who meet the major inclusion and exclusion criteria at randomization that may affect efficacy, who are not taking excluded concomitant medications during the study that could have an effect on efficacy (not including rescue¹²⁰ medication after Week 26), have the mRSS assessed at baseline and at least once during the main treatment phase and who are at least 80% compliant with study medication. A full definition of valid for PPS will be given in the SAP.

8.3 Variables

Efficacy variables are provided in Section 7.3 and safety variables are described in Section 7.5.

8.4 Statistical and analytical plans

8.4.1 Demographic and other baseline characteristics

Demographic variables and baseline characteristics will be summarized by treatment group for both analysis populations, that is, the FAS and PPS.

Medical history findings and AEs will be coded by Medical Dictionary for Regulatory Activities (MedDRA) codes and medications by Anatomical Therapeutic Chemical (ATC) codes (World Health Organization Drug Dictionary [WHO-DD]).

8.4.2 Efficacy - amended

In the efficacy analyses, countries and centers will be clustered by geographic region. The decision on country pooling will be made before unblinding. Statistical analyses will be adjusted for these countries / geographic regions.

8.4.2.1 Primary endpoint¹²¹

The primary analysis will be the change in mRSS from baseline to all assessments post baseline up to Week 52 using mixed model repeated measures (MMRM) with baseline mRSS as a covariate, fixed effects treatment arm and region, the interaction effect between study visit and treatment arm, and patient specific random effects to account for both heterogeneity among patients and correlation among measurements taken on the same patient with an unstructured covariance assumption. The main estimand of interest is the treatment difference

¹²⁰ Per Amendment 1

¹²¹ Per Amendment 4

between the riociguat and placebo treatment arms at Week 52. The null hypothesis to be tested is no difference between riociguat and placebo at this visit.

The model statement is:

$$Y_{ij} = \mu + \beta X_i + t_k + r_l + v_j + (tv)_{jk} + s_i + \varepsilon_{ij}$$

where Y_{ij} is the change from baseline in mRSS to visit j for subject i that is in treatment group k and region l ; μ is the intercept, β is the baseline covariate effect, X_i is the baseline mRSS for subject i , t_k is the fixed effect of treatment k , r_l is the fixed effect of region l , v_j is the fixed effect of visit j , $(tv)_{jk}$ is the interaction effect of treatment k by visit j , s_i is the random effect of subject i and $\varepsilon_{ij} \sim \text{Normal}(0, \sigma^2)$ represents the residual variance component with $\text{corr}(\varepsilon_{ij}, \varepsilon_{ij'}) = \rho_{jj'}$, $j \neq j'$

As a sensitivity analysis, the MMRM using the above model will also be applied to assessments post-baseline up to termination of study medication or initiation of rescue medication. In addition, the MMRM on all assessments will be repeated including additional effects time on rescue medication and time on study medication. MMRM assumes missing at random; mRSS by time of patient discontinuation from study medication¹²² will be summarized and further methods using multiple imputation that allow for missing data not at random will be investigated. Details of such methods will be described in the SAP.

An additional univariate sensitivity analysis will look at change in mRSS from baseline to Week 52 / last visit using analysis of covariance (ANCOVA) with baseline mRSS as a covariate, treatment arm and region as main effects. Last visit is defined as the last visit on treatment which in the case of premature termination of study medication is the termination visit. In the case of rescue¹²³ medication, the last visit is the visit where the decision is made to start rescue¹²⁴ medication with efficacy being assessed prior to escape medication starting. As a robustness analysis, a stratified (by region) non-parametric Wilcoxon test comparing riociguat and placebo will also be performed. In addition, and consistent with the primary analysis, a further ITT sensitivity endpoint analysis of change in mRSS to Week 52 / last visit will include all measurements recorded up to Week 52 or the termination visit, including those while rescue¹²⁵ medication was taken or if the patient returned after termination for a later visit up to Week 52.

Rules for the imputation of missing values where the patient discontinues the study (withdrawal of consent or death) or the study medication¹²⁶ for the univariate analysis, null / alternative hypothesis statements, and model statements in mathematical notation will be specified in the SAP. Two-sided 95% confidence intervals of treatment (riociguat compared to placebo) differences will be calculated in addition to the statistical significance testing.

¹²² Per Amendment 4

¹²³ Per Amendment 1

¹²⁴ Per Amendment 1

¹²⁵ Per Amendment 1

¹²⁶ Per Amendment 4

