1.2 Rationale of the study

Diffuse cutaneous SSc is one of the most severely incapacitating and life-threatening rheumatic diseases. Fibrosis of the skin and internal organs is a hallmark of the disease and the progression of the fibrosis disrupts tissue architecture and causes organ failure, resulting in high morbidity and mortality among patients with SSc.

Based on preclinical *in vitro* and *in vivo* data demonstrating that riociguat was safe and efficacious in different models of fibrotic diseases including scleroderma, the hypothesis is that riociguat may bring significant clinical benefit to patients with scleroderma by acting not only by improving vascular disease but, most importantly, by its inhibition of biochemical fibrotic pathways.[8] Based on the preclinical data, it is anticipated that riociguat may slow down the progression of the fibrotic disease by acting through TGF β -mediated pathways and, by its vasoactive properties, decrease the number and severity of Raynaud's attacks as well as decrease digital ulcer net burden.

This study aims to recruit patients with dcSSc. The rationale is: a) there is a better understanding of the natural history of dcSSc than lcSSc, and b) dcSSc is a subset of SSc in which more rapid progression in disease occurs with worse prognosis, and where there is a high unmet need for effective treatment.

To better design this study with regard to the inclusion criteria, a recent study [14] was taken into consideration and predictive parameters were identified for the progression of skin fibrosis within 1 year in patients with dcSSc. An observational study using the EUSTAR (EULAR Scleroderma Trials and Research) database was assessed. Worsening of skin fibrosis was defined as increase in modified Rodnan skin score (mRSS) > 5 points and $\geq 25\%$ from baseline to the second visit. Inclusion criteria were dcSSc, ACR criteria fulfilled, mRSS ≥ 7 at the baseline visit, valid data for mRSS at the second visit, and available follow up of 12 (± 2) months. In the univariate analysis, patients with progressive fibrosis were compared to non-progressors and predictive markers with $p < 0.2$ were included in the logistic regression analysis. The prediction models were then validated in a second cohort.

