A total of 637 dcSSc patients were eligible. Univariate analyses identified joint synovitis, short disease duration (≤ 15 months), short disease duration in females/patients without creatine kinase (CK) elevation, low baseline mRSS ($\leq 22/51$), and absence of esophageal symptoms as potential predictors for progressive skin fibrosis. In the multivariate analysis, by employing combinations of the predictors, 17 models with varying prediction success were generated, allowing cohort enrichment from 9.7% progressive patients in the whole cohort to 44.4% in the optimized enrichment cohort. Using a second validation cohort of 188 dcSSc patients, short disease duration, low baseline mRSS, and joint synovitis were confirmed as independent predictors of progressive skin fibrosis within 1 year showing a 4.5-fold increased prediction success rate.

From the 17 models generated by the multivariate analysis, the combination of 2 predictors, short disease duration, and low baseline mRSS, which allowed for a cohort enrichment of around 20%, was chosen.

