5.1 Eligibility

5.1.1 Inclusion criteria - amended

Patients must meet the following criteria to be eligible for enrollment in the study:

1. Written informed consent
2. Men or women aged 18 years and older
3. Systemic sclerosis, as defined by ACR/EULAR 2013 criteria[1]
4. dcSSc according to the LeRoy criteria[3] ie, skin fibrosis proximal to the elbows and knees in addition to acral fibrosis²².
5. Disease duration of ≤ 18 months (defined as time from the first non-Raynaud's phenomenon manifestation)
6. ≥ 10 and ≤ 22 mRSS units at the screening visit
7. FVC $\geq 45\%$ of predicted at screening
8. DL_{CO} $\geq 40\%$ of predicted (hemoglobin-corrected) at screening
9. Negative serum pregnancy test in a woman of childbearing potential at the screening visit
10. Women of childbearing potential must agree to use adequate contraception when sexually active. "Adequate contraception" is defined as any combination of at least 2 effective methods of birth control, of which at least 1 is a physical barrier (eg, condom with hormonal contraception like implants or combined oral contraceptives, condom with intrauterine devices). This applies since signing of the informed consent form until 30 (+5) days after the last study drug administration.
11. Ability to comply with the clinical visits schedule and the study-related procedures

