6.2.5 Subgroup analysis

Descriptive analyses of the primary efficacy outcome measure (change in mRSS from baseline to the end of the study and change in mRSS from Week 52 to end of study) will be performed for the following subgroups:

- region (North America, Europe and Australia/New Zealand, East Asia)
- gender (males/females)
- age (age < 65 years/age \geq 65 years)
- mRSS at baseline (10 - 16 units/17 - 22 units)
- disease duration at baseline (0 - 6 months, 7 - 12 months, 13 - 18 months)
- antibody at baseline:
 - SCL-70, RNA polymerase III; both positive, both negative, either one positive
 - Anti-centromere B; negative (< 10 U/mL) / positive (\geq 10 U/mL)
 - Anti-centromere B positive + SCL-70 and RNA polymerase III negative
 - Anti-centromere B positive + either SCL-70 or RNA polymerase III positive
- ILD (interstitial lung disease) per medical history (defined with preferred terms: interstitial lung disease and pulmonary fibrosis) at baseline (yes/no)
- FVC%, predicted at baseline (<50, 50-75, > 75)
- FVC%, predicted at week 52 (<50, 50-75, > 75)
- hsCRP elevated at baseline (\leq 3.0 mg/L, > 3.0 mg/L; and \leq 10.0 mg/L, > 10.0 mg/L)
- use of corticosteroids at baseline (yes/no)

- tendon friction at baseline (yes/no)
- mRSS at week 52 (<10 units/ 10 - 16 units/ 17 - 22 units/ >22 units)

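### The primary model could also adjust for disease duration and baseline joint findings, which the protocol names as predictors of skin worsening; this would be an efficiency gain of unknown size, not the repair of an error

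*Protocol*

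**What the plan says.** Protocol 8.4.2.1 models change in mRSS at all post-baseline visits up to Week 52 "with baseline mRSS as a covariate, fixed effects treatment arm and region". The remaining terms are visit, treatment by visit and a subject effect. The ANCOVA sensitivity analysis in the same section has baseline mRSS, treatment and region. Under 8.4.2.2 the continuous secondary variables follow the same models.

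Protocol 1.2 uses a registry study to choose the entry criteria. In its validation cohort of 188 patients, "short disease duration, low baseline mRSS, and joint synovitis were confirmed as independent predictors of progressive skin fibrosis within 1 year". The outcome there was binary: "Worsening of skin fibrosis was defined as increase in modified Rodnan skin score (mRSS) > 5 points" together with a rise of at least 25%.

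Both omitted variables can be had at entry:
- **Duration.** Protocol 5.1.1 requires "Disease duration of ≤ 18 months". The extension SAP, section 6.2.5, lists it as a descriptive subgroup: "disease duration at baseline (0 - 6 months, 7 - 12 months, 13 - 18 months").
- **Joints.** Protocol 7.6.14: "This physician-reported tool evaluates 28 joints for swelling and tenderness". It is done at screening and Week 52. No eligibility criterion restricts joint findings.

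Protocol 6.3 allocates permuted blocks to a country or group of countries and has no further stratification factor.

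**The concern.** Of three predictors that the protocol itself calls independent, only baseline mRSS enters the analysis. Independence is the relevant property, because the question is whether a variable adds anything to a model that already contains baseline mRSS. The protocol gives no reason for leaving the other two out.

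In a linear model, adjusting for a prognostic baseline variable leaves the target of estimation unchanged and reduces the residual variance. It also corrects for chance imbalance in that variable, which the randomization does not balance here.

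Power is not generous. Protocol 8.6 accepts 70% to 80%, allows for only two untreated patients with no inflation for dropout, and notes that the cited trials never reached a 4-point advantage. All five hierarchical secondary tests depend on a significant primary result. A modest gain at no data cost would therefore be worth having.

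**Working it through.** **Inputs from Protocol 8.6:** difference 4 points, SD 8 with no credit for covariates, two-sided 5%, 1:1, 51 to 64 per arm.

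**Assumed input:** joint partial R-squared of duration and joint count, given the terms already in the model. The documents state none, so a range of 0 to 0.10 is used, with SD 8 taken as the residual SD before the two variables are added.

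**1. Reproducing Table 8-2.** Two-sample t-test, noncentrality = 4 / (8·√(2/n)), with 2n − 2 degrees of freedom:

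| n per arm | 51 | 53 | 56 | 58 | 61 | 64 |
|---|---|---|---|---|---|---|
| Stated power (%) | 70 | 72 | 74 | 76 | 78 | 80 |
| Recomputed (%) | 70.6 | 72.2 | 74.6 | 76.1 | 78.2 | 80.2 |

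The table reproduces.

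**2. Adding the two covariates.** Residual SD = 8·√(1 − R²), with two fewer error degrees of freedom. For R² = 0.05 this is 8·√0.95 = 7.80, and at n = 64 the noncentrality is 4 / (7.80·√(2/64)) = 2.90.

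| Assumed R² | Residual SD | Power, 64 per arm | Power, 51 per arm | n per arm for 80% | 95% CI half-width, 64 per arm |
|---|---|---|---|---|---|
| 0 | 8.00 | 80.1% | 70.5% | 64 | 2.80 |
| 0.02 | 7.92 | 80.9% | 71.4% | 63 | 2.77 |
| 0.05 | 7.80 | 82.1% | 72.7% | 61 | 2.73 |
| 0.10 | 7.59 | 84.1% | 75.0% | 58 | 2.66 |

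**3. Break-even.** Fitting two covariates that explain nothing costs about 2/(N − 4) of the variance: 2/124 = 1.6% for N = 128 and 2/98 = 2.0% for N = 102. A joint R² below that brings no net gain. The table in step 2 deducts only the degrees of freedom, so its low end is slightly generous. Multiplying the variance by (N − 3)/(N − 5), which is 125/123 at N = 128 and 99/97 at N = 102, takes the R² = 0 powers to 79.5% and 69.7%.

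**4. The same gain seen as chance imbalance.** The unadjusted estimate shifts with SD 8·√R²·√(2/n). At 64 per arm, one trial in 20 would shift by at least 1.96 × 8 × √0.05 × √(2/64) = 0.62 points for R² = 0.05, or 0.88 points for R² = 0.10. That is 15.5% and 22% of the 4-point target. This is not a further benefit on top of step 2: the unadjusted standard error already includes this variation.

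**5. Where in the range?** Three features of the documents point to the low end:
- The predictors were found for a binary worsening event, and the endpoint is mean change.
- Eligibility stops at 18 months. The registry study's univariate cut was 15 months, so most of the contrast between short and long duration is removed at entry.
- Synovitis is seen only through the joint count.

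Against this, joint findings keep their full spread because nothing in eligibility restricts them, so they are the likelier source of any gain. The registry figures of "cohort enrichment from 9.7% progressive patients in the whole cohort to 44.4% in the optimized enrichment cohort" cannot be turned into an R² for synovitis, because the protocol does not say how much of that rise is due to synovitis.

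**The case against.** The strongest case against is that nothing is broken. The model contains the baseline value of the outcome and the geographic factor behind the blocking. Omitting further covariates causes no bias and no type I error inflation, and the sample size takes no credit for covariates. All of that stands.

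It is also fair to say that duration has already been used through eligibility, that no R-squared is documented, and that a gain of zero is possible. Those objections limit the size of the point. They do not explain why predictors described as independent and validated were left out.

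Two further objections limit what can be done. The main-phase SAP is a separate document that was not supplied, so a supportive adjusted model may exist there. The extension SAP's duration subgroup shows that the variable is available, but it says nothing about the primary analysis. And the time for pre-specification has passed: the extension SAP says that the main-phase SAP was finalized before unblinding and dates its version 4.0 to 22 Dec 2017, while Protocol Amendment 7 of 17 Apr 2018 was itself prompted by the main-phase results.

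A reader might infer three stronger things. One is that precision has demonstrably been lost; without an R-squared, that is not shown. Another is that the strongest predictors were left out; Section 1.2 gives no effect sizes or ranking. The third is that uncorrected chance imbalance undermines the result; the randomized comparison and its standard error already allow for it.

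**Conclusion.** The point holds as an efficiency improvement. The primary MMRM and the ANCOVA omit two variables that the protocol's own rationale identifies as predictors of skin worsening, although duration and a usable proxy for synovitis are available at entry. The estimate and the test are valid as planned.

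For an assumed joint R-squared of 0 to 0.10 the gain is 0 to about 4 power points at 64 per arm and 0 to about 4.5 at 51 per arm, or at most 6 patients per arm (64 − 58). Below about 1.6% to 2.0% there is none. These figures rest on the assumed range, on the SD of 8, and on treating the primary comparison as a two-sample comparison at Week 52, as the sample size does. The true value may well be near the low end.

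**What to change.** In the design as written, pre-specify baseline disease duration (months, continuous) and screening swollen joint count, as a proxy for synovitis, as covariates in the primary MMRM and the ANCOVA. Keep the mRSS-and-region model as a sensitivity analysis. State in advance how the joint count enters the model and how joints coded as replaced or not assessable (Protocol Appendix 14.3) are handled, since the documents give no cut-point. If the sponsor prefers to leave the variables out, a sentence of justification would do.

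For this trial's data, the primary model should not be changed now. An adjusted analysis may be reported beside it, labelled supportive and post hoc.

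The cost is two model degrees of freedom and a line or two of specification. No new data are needed. If the variables explain nothing, the loss is about 0.6 power points at 64 per arm (80.1% to 79.5%) and 0.8 at 51 (70.5% to 69.7%).
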